### **3.1.3 Physical examination**

Weight (kg) will be explored using the mean change from baseline longitudinally over time.

### **3.1.4 ECGs**

The outcome of the overall evaluation of 12-lead ECG measurements by the central reading will be assessed as normal or abnormal. It is the investigator's judgment whether the findings/results on the central ECG laboratory report are clinically relevant or not. The combination of both judgments leads to the following categories used for analysis:

- Normal
- Abnormal, not clinically significant
- Abnormal, clinically significant

If the overall evaluation by the investigator and the central ECG report don't match, the investigator's judgement will be used. In case of repeated measurements (triplicates) at a visit, the worst category at the respective visit will be used for the analysis, with "abnormal, clinically significant" defined as worse than "abnormal, not clinically significant," which in turn is worse than "normal."

Changes from baseline of the following variables will be explored:

- Heart rate (beats per minute)
- QRS duration (ms)
- PR interval (ms)
- RR interval (ms)
- QT (ms)
- QTcB (ms)
- QTcF (ms)

Potentially Clinically Significant post-baseline values or changes from baseline [REDACTED]. For some parameters, more than one criterion is given. The proportion of subjects meeting each criterion will be explored.

In case of repeated measurements (triplicates) at a visit, the mean of all non-missing values at the respective visit will be used for the analyses of the continuous ECG variables and the determination of Potentially Clinically Significant values.

### 3.1.5 Modified SELENA Flare Index based flares

A modification of the classic SELENA Flare Index using the SLEDAI-2K will be used as a safety outcome to characterise flares. The modified SELENA Flare Index-Based Flare Assessment Scale has 2 sets of definitions:

#### Mild/moderate flare

A mild/moderate flare is defined if at least one of the following criteria are met:

- Increase from previous visit in SLEDAI-2K of  $\geq 3$  points but less than 7 points
- At least 1 new or worse manifestation in
  - Discoid, photosensitive, profundus, cutaneous vasculitis, bullous lupus
  - Nasopharyngeal ulcers
  - Pleuritic
  - Pericarditis
  - Arthritis
  - Fever (SLE)
- Increase from previous visit in PGA of  $\geq 1$  but PGA value of  $\leq 2.5$  points

#### Severe flare

A severe flare is defined if at least one of the following criteria are met:

- Increase from previous visit in SLEDAI-2K of  $\geq 7$  points
- At least 1 new or worse manifestation in
  - Central nervous system SLE
  - Vasculitis
  - Nephritis
  - Myositis
  - Haemolytic anaemia  
defined as haemoglobin  $< 70$  g/L or decrease in haemoglobin  $> 30$  g/L with positive Coombs AND at least 1 of the following: decreased haptoglobin, increased total bilirubin not due to Gilbert's disease, increased reticulocyte count
- Hospitalization due to SLE disease activity
- Increase from previous visit in PGA to a value  $> 2.5$  points

The flare rate per subject year will be calculated separately for mild/moderate flares and severe flares as well as overall. The flare rate per subject year is defined as the number of subjects with a respective flare divided by the sum of exposure time in days (i.e., date of last dose of investigational product + 28 days - day of first dose of investigational product + 1 day) for all subjects in the analysis set multiplied by 365.25 days/year.

For analyses based on LTE data only (e.g. for subjects switching from Placebo to 300 mg anifrolumab in the “All Anifrolumab” treatment group), the first administration of investigational product during the LTE will be considered in the above. For analyses based on feeder study data only (e.g. for subjects switching from Placebo to 300 mg anifrolumab in the “All Randomised Placebo” treatment group), the minimum of last administration of investigational product in the feeder study + 28 days and first administration of investigational product in the LTE -1 day will be used in the above. If a subject discontinued the study or had the last follow-up visit earlier than expected, the date of study discontinuation/end of study will be used as the censoring date.

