#### **8.5.1 Analysis methods for safety variables**

Adverse events (AESIs and SAEs) will be summarised using incidence rates (ie, number of events divided by person-time at risk). The main treatment groups for addressing the primary objective will be “Randomised Anifrolumab 300 mg” and “Randomised Placebo”. In addition, rates will also be explored over time to describe potential changes in risks with longer exposure. All AEs will be listed.

Laboratory data for haematology and clinical chemistry will be summarised. The frequency of changes with respect to normal ranges between baseline and each post-treatment time point will be tabulated. Frequencies of clinically noteworthy values (defined in the SAP) occurring during the clinical study will also be given. Shifts from normal to abnormal between baseline and each post-baseline time point will be evaluated for urinalysis.

The rate of flares as defined by a modification of the SELENA Flare Index using the SLEDAI-2K (number of flares divided by person-time at risk) will be explored.

Other safety data will be summarised as appropriate. Further details will be provided in the SAP.

[REDACTED]

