#### 2.1.6 Treatment groups for analysis

Summaries will be presented according to the following combined treatment groups. If not mentioned otherwise, data from subjects discontinuing from the investigational product in studies D3461C00004 or D3461C00005, or who elect not to participate in the LTE, will be considered up to the adjusted analysis-defined visit window of Week 52 (ie, up to Day 378).

Primary:

- **Randomised Anifrolumab 300 mg:** Subjects randomised to anifrolumab 300 mg in studies D3461C00004 or D3461C00005 using all data from start of feeder study to end of LTE.
- **Randomised Placebo:** Subjects randomised to placebo in studies D3461C00004 or D3461C00005 using data from start of feeder study up until switch to anifrolumab 300 mg or to end of LTE for subjects re-randomised to placebo in LTE, respectively.

Supportive:

- **Placebo Feeder + Placebo LTE:** Subjects randomised to placebo in Studies D3461C00004 or D3461C00005 and re-randomised to placebo in LTE using all data from start of feeder study to end of LTE. Data from subjects not randomised into the LTE for any reason but that would have been re-randomised to placebo are included in this treatment group up to Week 52. Subjects who are not randomised into the LTE study will be assigned to Placebo or anifrolumab 300 mg via a

separate randomization process in order to determine who would have been re-randomised to placebo.

- **All Anifrolumab:** Subjects randomised to anifrolumab in studies D3461C00004 or D3461C00005, regardless of dose, and subjects randomised to placebo in studies D3461C00004 or D3461C00005 and then re-randomised to anifrolumab 300 mg in LTE, using all data from start of feeder study or switch to anifrolumab, respectively, to end of LTE. Baseline data from the feeder study will be included for all subjects.

Additional supportive:

- **Placebo Feeder + Anifrolumab 300 mg LTE:** Subjects randomised to placebo in studies D3461C00004 or D3461C00005 and then re-randomised to anifrolumab 300 mg in LTE using data from start of feeder study to end of LTE. Data from subjects not randomised into the LTE for any reason, but that would have been re-randomised to anifrolumab 300 mg are included in this treatment group up to Week 52. Subjects who are not randomised into the LTE study will be assigned to Placebo or anifrolumab 300 mg via a separate randomization process in order to determine who would have been re-randomised to anifrolumab 300 mg.

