Adverse events with missing intensity will be assumed to be severe. Events with missing relationship to study medication per the investigator will be assumed to be related. If no information about seriousness is available, the AE will be considered serious.

AEs and AEs leading to discontinuation of investigational product during treatment and follow-up will also be presented by time intervals of the first onset of the event. For this analysis, repeated events with the same preferred term will not be considered (i.e., if a subject has more than one event with the same preferred term, only the event with the earliest date of onset will be used). The following time intervals are defined for AEs during treatment and follow-up:

- Year 1:  
AEs with date of onset  $\geq$  date of first administration of investigational product and either  $<$  maximum of date of re-randomisation in LTE study and date of administration of IP in LTE study or from subjects who are not randomised into the LTE study (ie, all AEs documented in the Phase 3 feeder Studies D3461C00004 and D3461C00005 are considered AEs in Year 1). If the AE has an onset on the day of first dose of investigational product in the LTE and is recorded in the Phase 3 feeder studies, it will be considered during year 1.
- Year 2:  
AEs with date of onset  $\geq$  date of first administration of investigational product in LTE study and  $<$  date of first administration of investigational product in LTE study plus 364 days
- Year 3:  
AEs with date of onset  $\geq$  date of first administration of investigational product in LTE study plus 364 days and  $<$  date of first administration of investigational product in LTE study plus 728 days
- Year 4:  
AEs with date of onset  $\geq$  date of first administration of investigational product in LTE study plus 728 days and  $<$  date of first administration of investigational product in LTE study plus 1092 days
- After year 4:  
AEs with date of onset  $\geq$  date of first administration of investigational product in LTE study plus 1092 days

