If an AE has a missing onset date, then unless the stop date of the AE indicates otherwise, it will be assigned to the “Year 1” time interval. Similarly, if an AE has a partial onset date, then unless the partial onset date or the stop date indicates otherwise, it will be assigned to the earliest time interval given the available date information. If the missing or partial start date does not allow an assignment of the event as during the Phase 3 feeder studies or the LTE study, the AE will be assigned to “Year 1” if documented in one of the Phase 3 feeder studies or to “Year 2” if documented in the LTE.

The event rate per 100 subject years is defined as the number of subjects with an event divided by the sum of exposure time in days in the respective time period for all subjects in the analysis set multiplied by 365.25 days/year multiplied by 100. The exposure in a time period for each subject will be calculated as end of period – start of period + 1 (e.g., as the earlier of either (date of last dose of investigational product + 84 days, or date of study discontinuation) - date of first dose of investigational product + 1 day for the summary of all AEs during treatment and follow-up; for AEs during treatment, the same definition will apply, with the exception of last dose of investigational product + 28 days will be used). For analyses based on LTE data only (e.g. AE rates for subjects switching from Placebo to 300 mg anifrolumab in the “All Anifrolumab” treatment group), the first administration of investigational product during the LTE will be considered as the start of the overall period. For analyses based on feeder study data only (e.g. AE rates for subjects switching from Placebo to 300 mg anifrolumab in the “All Randomised Placebo” treatment group), the end of the overall period will be defined as the first administration of investigational product in the LTE -1 day. If a subject discontinued during a period or had the last follow-up visit earlier than expected, the date of study discontinuation/end of study will be used as end of the respective period.

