For AESIs, SAEs, and COVID-19 related analyses of AEs, additional analyses based on an alternative event rate per 100 subject years will be derived as the number of subjects with the respective AE divided by the sum of time at risk in days for all subjects in the analysis set multiplied by 36,525. The time at risk is defined as time (including start and end date) from start of period (e.g., date of first administration of investigational product for all AEs) to the date of first event, death, withdrawal of consent, or end of period, whatever comes first. The same considerations for analyses based on LTE/feeder phase 3 data only as defined above will apply for alternative event rates.

The time to first onset of a specific AESI category will be derived as date of first onset of any AE in the respective category – date of first administration of investigational product + 1. For time to event analyses based on LTE data only (e.g. for subjects switching from Placebo to 300 mg anifrolumab in the “All Anifrolumab” treatment group), the first administration of investigational product during the LTE will be used in the above. AEs with an onset date before the date of first administration of investigational product and AEs with an onset after 84 days after the date of last administration of investigational product will not be considered for the time to first onset of AESI. If a subject has no AESI in a specific category, the time to first onset will be censored at the date of last administration of investigational product + 84 days. For time to event analyses based on feeder study data only (e.g. for subjects switching from Placebo to 300 mg anifrolumab in the “All Randomised Placebo” treatment group), the

minimum of last administration of investigational product in the feeder study +84 days and first administration of investigational product in the LTE -1 day will be used in the above. If a subject discontinued the study or had the last follow-up visit earlier than expected, the date of study discontinuation/end of study will be used as the censoring date.

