### **4.2.1 Analysis of the primary variables (safety variables)**

If not stated otherwise, safety variables will be summarised by combined treatment group for the full analysis set.

The primary assessment will be the comparison between the treatment groups “Randomised Anifrolumab 300 mg” and “Randomised Placebo”. The “All Anifrolumab” treatment group will be used to assess rare events.

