#### **4.2.1.5 Flares based on Modified SELENA Flare Index**

The flare rate per subject year will be presented for mild/moderate flares, severe flares, and any flares.

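### SAP 3.1.5 replaces the protocol's flare rate (flares over person-time at risk) with flaring subjects over total exposure, which makes the longer-followed anifrolumab 300 mg group look better in the pooled comparison.

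*SAP*

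**What the plan says.** Protocol 8.5.1 plans a flare rate by the modified SELENA Flare Index, given as "number of flares divided by person-time at risk) will be explored".

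SAP 3.1.5 states: "The flare rate per subject year is defined as the number of subjects with a respective flare divided by the sum of exposure time". Exposure is in days and runs from first dose to last dose plus 28 days, for all subjects in the analysis set. It does not stop at the first flare. The same section gives exposure rules for feeder-only and LTE-only data. SAP 4.2.1.5 adds only this: "The flare rate per subject year will be presented for mild/moderate flares, severe flares, and any flares".

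The SAP rule has the form of the general AE event rate in SAP 3.1.1, "the number of subjects with an event divided by the sum of exposure time in days". For AESIs, SAEs and COVID-19 analyses, SAP 3.1.1 adds an alternative rate whose time at risk runs "to the date of first event, death, withdrawal of consent, or end of period, whatever comes first". Flares are not named there.

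SAP 4.2.1 summarises safety variables by combined feeder + LTE group unless stated otherwise. It adds that "The primary assessment will be the comparison between the treatment groups" Randomised Anifrolumab 300 mg and Randomised Placebo. SAP 2.1.6 follows the first group to the end of the LTE. For placebo subjects who switch, it defines the second group "using data from start of feeder study up until switch to anifrolumab 300 mg".

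**The concern.** The SAP measure is neither an event rate nor a first-event rate. Its numerator cannot exceed one per subject, while its denominator keeps growing after the flare. With no true difference, the group followed longer therefore shows the lower value. The two groups in the primary assessment differ in follow-up by design, because half of the placebo subjects who enter the LTE leave the placebo group at the switch.

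The pooled table could show fewer flares on anifrolumab when there is no effect, or hide a true increase. The AE tables do not make up for this: under protocol 6.6.7, worsening of SLE is reported as an AE only if it meets the criteria for an SAE.

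**Working it through.** **Inputs.** Annual dropout is 20% (300 mg) and 30% (placebo), and 90% of completers enter the LTE (protocol 8.2, SAP 1.3). Placebo entrants are re-randomised 1:1 (SAP 1.2). The feeder lasts one year and the LTE three. Assumed here: dropout spread evenly within each year, and a constant flare rate L that is the same in both groups.

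**Step 1: reproduce the plan's follow-up.** Mean years per subject:
- 300 mg: 0.90 + 0.8 × 0.9 × 0.90 × (1 + 0.8 + 0.64) = 2.481
- Randomised Placebo: 0.85 + 0.7 × 0.9 × 0.5 × 0.85 × (1 + 0.7 + 0.49) = 1.436
- Placebo Feeder + Placebo LTE: 0.85 + 0.7 × 0.9 × 0.85 × 2.19 = 2.023

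The stated 893 and 517 subject-years, divided by 2.481 and 1.436, both give about 360 subjects. That size is back-fitted, not stated. With 360 per group the model returns 893.2 and 517.1. Placebo Feeder + Placebo LTE (180) gives 364.1.

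**Step 2: SAP measure with every flare detected.** Measure = sum of (1 − exp(−L·t)) over subjects, divided by the sum of t. The correct ratio is 1.00.

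| L per year | Subjects with a flare, 300 mg | Subjects with a flare, Randomised Placebo | Ratio vs Randomised Placebo | Ratio vs Placebo Feeder + Placebo LTE |
|---|---|---|---|---|
| 0.05 | 41.2 | 24.4 | 0.98 | 0.99 |
| 0.2 | 131.4 | 83.2 | 0.91 | 0.97 |
| 0.5 | 225.3 | 159.6 | 0.82 | 0.93 |
| 1.0 | 284.8 | 229.6 | 0.72 | 0.89 |

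Example at L = 0.5: (225.3/893.2) / (159.6/517.1) = 0.252/0.309 = 0.82.

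A true 25% excess on 300 mg (0.625 vs 0.5) would read 0.90 against Randomised Placebo and 1.02 against Placebo Feeder + Placebo LTE. Unequal dropout is not the main cause: with 20% or 30% dropout in both groups (exponential dropout), the ratio against Randomised Placebo is still 0.87 to 0.88 at 0.5 per year. With all flares over person-time, the same model gives 1.00 at every rate.

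**Step 3: assessment schedule (conditional).** Protocol Tables 2 and 3 schedule the index at LTE Weeks 12, 24, 36 and 52, then at 76, 104, 128 and 156. If each assessment captures only the past 28 days (protocol 5.2.8), coverage is 4 × 28/364 = 0.308 in LTE year 1 and 2 × 28/364 = 0.154 in each later year. The feeder schedule is not in the documents. It is assumed to be 4-weekly (coverage 1.0) or 12-weekly (0.308).

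Person-years by year are 324.0, 233.3, 186.6 and 149.3 (300 mg) and 306.0, 96.4, 67.5 and 47.2 (Randomised Placebo). All recorded flares over pooled person-time, per unit of true rate:
- 4-weekly feeder: 447.5/893.2 = 0.501 vs 353.3/517.1 = 0.683, ratio 0.73
- 12-weekly feeder: 223.2/893.2 = 0.250 vs 141.5/517.1 = 0.274, ratio 0.91

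Against Placebo Feeder + Placebo LTE these ratios are 0.91 and 0.96. On the same reading, at 0.2 to 1.0 flares per year, the SAP measure against Randomised Placebo is 0.66 to 0.72 (4-weekly) and 0.83 to 0.90 (12-weekly). The definition then adds about 0.02 to 0.08 to a distortion that the schedule already causes. Within a single year the all-flares ratio is 1.00, if dropout is unrelated to flare risk and attendance is equal.

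**The case against.** Flares are one of the other safety variables, to be explored without a formal comparison. Serious worsening still reaches the SAE tables. At 0.05 flares per year the bias is about 2%. The combined tables also show Placebo Feeder + Placebo LTE, where the bias is smaller. Protocol 8.3.3 promises supplemental LTE-only summaries, SAP 2.1.6 defines LTE-only groups, and SAP 3.1.5 has exposure rules for them. On LTE data alone, the SAP measure for 300 mg against Placebo Feeder + Placebo LTE would read 0.96 at 0.5 and 0.93 at 1.0 flares per year. All of this stands and keeps the priority low. It does not remove the problem, because SAP 4.2.1.5 commits to no LTE-only or time-at-risk flare output and SAP 4.2.1 defaults to the combined groups.

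A reader might infer three stronger things that the documents do not support:
- **The departure from the protocol went unrecorded, or no other flare analysis exists.** SAP Section 6 is partly redacted and SAP 3.2 and 4.2.2 are not in the public text, so neither can be known. No weight rests on Section 6.
- **Sparser assessment certainly biases any pooled rate.** That rests on the 28-day look-back in protocol 5.2.8. The flare criteria in SAP 3.1.5 compare with the previous visit, state no 28-day limit, and include hospitalisation for SLE. If an assessment covers the whole interval since the last one, the bias is smaller.
- **Restoring the protocol formula cures everything.** It removes the saturation in step 2, but not the schedule effect in step 3 if that effect is real.

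**Conclusion.** The two definitions contradict each other. In the pooled primary comparison, the SAP version favours the longer-followed 300 mg group when true flare rates are equal. The ratio would read 0.98 to 0.72 against Randomised Placebo, and 0.99 to 0.89 against Placebo Feeder + Placebo LTE, over assumed rates of 0.05 to 1.0 flares per year. These sizes rest on the planning dropout and entry rates, a constant flare rate common to both groups, and full detection. Because the documents give no flare rate, they illustrate direction and scale and do not predict the result. Confidence is high on the definition and the direction of its bias, and lower on the schedule effect. The consequence is for the reading of an exploratory safety table, not for any error rate. It should be corrected, at low priority.

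**What to change.** In SAP 3.1.5 and 4.2.1.5, use number of flares over person-time at risk as in protocol 8.5.1, with a rule for repeat flares, for example at most one per assessment. Commit to presenting it separately for the feeder period and for the LTE-only groups of SAP 2.1.6, not only as one pooled rate. SAP 3.1.5 already holds the feeder-only and LTE-only exposure rules.

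Optional: also report the rate by the Year 1 to Year 4 intervals that SAP 3.1.1 introduces with "The following time intervals are defined for AEs during treatment and follow-up". This guards against the change in assessment frequency.

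**Cost.** SAP wording and some reprogramming, with no new data. Splitting by year costs precision. With the 95% interval factor taken as exp(1.96/√flares), Randomised Placebo at 0.5 flares per year goes from 1.13 either side (517 subject-years pooled) to 1.33, 1.40 and 1.50 in Years 2 to 4 with full detection. Under the 28-day look-back only about 14.8, 5.2 and 3.6 flares would be recorded in those years, and the factors become about 1.66, 2.36 and 2.80. They are wider still if repeat flares within a subject are correlated. For that reason the by-year split is an option and the feeder/LTE split is the core request.

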#### 4.2.1 Premature discontinuation of investigational product

Subjects who prematurely discontinue investigational product (see Section 3.9.1) will be asked to return for all regularly scheduled clinic visits. If the subject is unwilling to complete all regularly scheduled clinic visits, the subject should complete the Early Discontinuation Visit (EDV, Week 156) within 4 weeks after the last administration of investigational product, as well as Follow-up Visit 1 and Follow-up Visit 2 (8 and 12 weeks after the last dose of investigational product) unless consent is withdrawn. If the subject is unwilling to continue with any study visits, including EDV, or is willing to continue with only selected study assessments, at a minimum, the following assessments should be completed:

- AEs including AESIs and SAEs
- [REDACTED]
- Serum chemistry, haematology, urinalysis
- Urine for protein, creatinine, and urine-protein-creatinine ratio
- Vital signs
- Physical examination, weight
- [REDACTED]
- [REDACTED]
- Concomitant medications
- Blood test for TB
- Pap smear test (female subjects with an intact cervix only)

If the subject does not agree to do this, they will be asked if they can be followed on a monthly basis via telephone calls. At these calls, they will be asked about AEs/SAEs, lupus symptoms, and lupus medications.

Adverse events will be followed up per Section 6.6.2.

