#### 3.1 Safety variables

The following primary safety data will be collected: AESIs and SAEs.

Other safety variables include adverse events (AEs), vital signs, physical examination, electrocardiograms (ECGs), flares as defined by a modification of the SELENA Flare Index using the SLEDAI-2K, haematology, clinical chemistry, and urinalysis.

Change from baseline to each post-treatment time point where scheduled assessments were made will be calculated for relevant measurements.

If not stated otherwise, on-treatment values are defined as values with an assessment date after the first administration of investigational product and on or before the date of last administration of investigational product + 28 days.

The restriction that “data from subjects discontinuing from the investigational product in studies D3461C00004 or D3461C00005, or who elect not to participate in the LTE, will be considered up to the adjusted analysis-defined visit window of Week 52 (ie, up to Day 378)” (see section 2.1.6) does only apply to visit-based analyses of safety variables.

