## **4.2 Analysis methods**

Where applicable, the analyses will include data from randomisation in the Phase 3 feeder studies until the end of the LTE study, regardless of whether study treatment was prematurely discontinued or delayed, and/or irrespective of protocol adherence.

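### The SAP's flare rate stops person-time at last dose + 28 days but puts no date limit on the flares counted, so numerator and denominator can cover different periods

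*SAP*

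**What the plan says.** SAP 3.1.5 (end of the severe flare text) defines the rate as "number of subjects with a respective flare divided by the sum of exposure time in days". The exposure time in brackets is "date of last dose of investigational product + 28 days - day of first dose of investigational product + 1 day". For early exit it adds that "the date of study discontinuation/end of study will be used as the censoring date". SAP 4.2.1.5 only lists the flare categories to be presented and gives no window.

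The general rules on which data enter are broad:

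- SAP 4.2 includes data to the end of the LTE "regardless of whether study treatment was prematurely discontinued or delayed, and/or irrespective of protocol adherence", where applicable.
- SAP 4.1.2 says that analyses not tied to a particular visit use all data unless otherwise specified. SAP 4.1.3 says the same of presentations that are not by visit.
- The Day 378 cut-off for subjects who do not continue "does only apply to visit-based analyses of safety variables" (SAP 3.1), so it does not limit the flare rate.

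Subjects who stop drug early "will be asked to return for all regularly scheduled clinic visits" (Protocol 4.2.1), and Protocol 3.9.5 encourages them to complete all procedures. Protocol Tables 2 and 3 schedule the Modified Flare Index at LTE Weeks 0, 12, 24, 36, 52, 76, 104, 128 and 156.

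**The concern.** A rate needs events and person-time from the same period. Here the denominator ends 28 days after the last dose, while nothing ends the numerator. Take a hypothetical subject whose last dose is at LTE Week 8, who keeps attending, and whose first LTE flare is scored at LTE Week 52. In an LTE-only rate this subject adds one to the numerator and 8 + 4 = 12 weeks to the denominator, although the flare was found after 52 weeks of observation.

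The sentence on study discontinuation does not cure this. It is worded for early exit from the study, and it adds no time for someone who is off drug and completes the study.

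At stake are the reported level of the flare rate and its reproducibility, because two programmers could defend different numerators.

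**Working it through.** **Text comparison.** The SAP matches windows where it means to. For adverse events (3.1.1), onset windows end at last dose + 28 or + 84 days, and the exposure for those event rates ends on the same dates. The on-treatment definition in SAP 3.1 is invoked for ECG shifts (4.2.1.4) and for laboratory and urinalysis shifts and the Hy's Law table (4.2.1.6). It is not invoked in 3.1.5 or 4.2.1.5. SAP 4.2.3.1 also plans to report subjects who are off drug but still on study, so such subjects are expected.

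**Size.** The documents give no flare rate, so there is no figure to reproduce.

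Inputs from the documents: annual dropout of 30% (placebo) and 20% (anifrolumab 300 mg), with 90% of feeder completers entering the LTE (SAP 1.3); 1:1 re-randomisation of placebo subjects, with Randomised Placebo cut at the switch (SAP 2.1.6); and the LTE flare visits above.

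Assumptions, not in the documents: the dropout rates stand in for stopping drug; stopping times are exponential; flare assessments in the feeder studies are 4-weekly; a visit detects a flare from the prior 4 weeks; the flare hazard is 0.3 to 1.0 per year, equal in both groups and the same on and off drug; and a share s of those who stop drug stay in visits.

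Inflation = (subjects with a flare at any observed visit) / (subjects with a flare by the denominator's end date), with the same denominator in both rates.

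| Share s staying in visits | Randomised Anifrolumab 300 mg | Randomised Placebo |
|---|---|---|
| 0 | none | none |
| 25% | 3-4% | 4-5% |
| 50% | 6-7% | 8-10% |
| 100% | 11-15% | 16-20% |

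With all staying, the anifrolumab:placebo ratio falls by about 4%.

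**Check with continuous observation and lower hazards.** Let λ be the flare hazard, t the time of the last dose, e the denominator's end (t + 28 days, capped at end of follow-up) and T the end of follow-up (year 1 in the feeder study, year 4 in the LTE). A subject contributes 1 − exp(−λe) expected first flares in the window. After it, the subject contributes s·exp(−λe)·[1 − exp(−λ(T − e))]. Person-time is e. These are averaged over t, LTE entry and the switch. For λ = 0.2 per year and s = 100%, per subject:

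- Anifrolumab 300 mg: 0.369 in window, 0.078 after it, 2.512 years. Matched rate 0.369/2.512 = 0.147; unrestricted (0.369 + 0.078)/2.512 = 0.178, or +21%.
- Randomised Placebo: 0.235, 0.063, 1.459 years. Matched 0.235/1.459 = 0.161; unrestricted 0.298/1.459 = 0.204, or +27%.

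Over λ = 0.1 to 0.4 and s = 25% to 100%, inflation is 4-23% on anifrolumab and 5-30% on placebo. At λ = 0.2 the placebo:anifrolumab ratio moves from 1.09 to between 1.11 and 1.15.

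**Unequal retention.** With s = 50% on anifrolumab and 25% on placebo, the continuous model at λ = 0.2 gives 11% against 7%. The visit-schedule model gives 6-7% against 4-5% at hazards of 0.3 and 0.5. The order reverses.

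**The case against.** **An on-treatment reading is open.** SAP 3.1, which governs 3.1.5, says "on-treatment values are defined as values with an assessment date after the first administration of investigational product" and up to last dose + 28 days, the same limit as the flare denominator. Terms such as exposure time and censoring date suggest a single analysis period, and the rule in SAP 4.2 is qualified. This stands in part: the sponsor may have intended matched windows. But the flare sections never apply that definition, other sections do, and the defaults point to all data. The literal rule therefore gives a mismatched rate.

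**A reader might infer that the error favours anifrolumab.** The documents do not support this. The 30% and 20% are planning figures for dropout, used to project follow-up. They do not describe subjects who stop drug and stay in visits, and someone who leaves the study adds no later flares. No off-drug retention by group is given, and unequal retention can reverse the direction.

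**A reader might also infer that the rate exceeds the true flare hazard.** That does not follow. Each subject counts once and time does not stop at the first flare, which pulls the rate down. In the continuous model with a true hazard of 0.3 and full retention, the unrestricted rates are about 0.23 and 0.27. The overstatement is only against a matched-window rate.

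**A larger distortion remains.** With matched windows and equal hazards of 0.3, 0.5 and 1.0, the continuous model already gives an anifrolumab:placebo ratio of about 0.88, 0.82 and 0.72. The mismatch moves it to about 0.84, 0.79 and 0.69 under full retention. This is correct, but it comes from counting subjects over unstopped time, where Protocol 8.5.1 has number of flares over person-time at risk. It is a separate point that this fix does not address.

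**Weight.** Flares are an other safety variable, no formal comparison is planned, and 4.2.1.5 specifies no confidence interval. This limits the consequence but does not remove the defect.

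**Conclusion.** The point holds as a mismatch of windows in SAP 3.1.5. The denominator ends at last dose + 28 days, the numerator has no limit, and the SAP's general rules would bring in flares seen after stopping drug. In the visit-schedule illustration, across both groups, the rate is overstated relative to a matched-window rate by 3-5% at a quarter retention, 6-10% at half and 11-20% if all stay. There is no overstatement if everyone who stops drug leaves the study. These sizes rest on assumed flare hazards, an assumed feeder schedule and dropout used as a stand-in for stopping drug; with lower hazards and continuous observation the percentages are somewhat higher. A larger effect on placebo requires both higher placebo discontinuation and similar off-drug retention, and neither is shown. The change is worth making because it is cheap. It does not touch the primary AESI and SAE rates.

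**What to change.** In SAP 3.1.5, state one window for both parts: count only subjects with a flare assessed from first dose to the date at which the denominator ends, namely last dose + 28 days, or the switch to anifrolumab or study discontinuation if earlier. For LTE-only rates, start both parts at the first LTE dose. This uses the limit already in SAP 3.1. Adding the 7-day visit window is unnecessary and would create a + 35-day limit found nowhere else in the SAP.

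Optionally, add a treatment-policy version in which flares and person-time both run to the last flare assessment, still cut at the switch for Randomised Placebo.

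The cost is one sentence and a date filter. The downside is that post-treatment flares, including any scored at a visit just after the 28 days, drop out of the main rate and appear only in the optional version or in listings.
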